#### Abstract:

**Background**: Carrot cultivars with a high content of falcarinol and falcarindiol have a strong antineoplastic effect in primed rats. The necessary corresponding blood concentration can easily be obtained in humans. High intake of carrots has been shown to reduce bowel cancer in humans in prospective cohort studies, and carotenes have been shown not to have any effect. A prophylactic effect against other cancers in humans especially of the lung and pancreas has also been indicated (1).

Patients who had polyps resected that are considered high risk will be offered a follow up (FU) colonoscopy after 1 year and after 3 years according to national guidelines. At this FU, about 30-40% of them will present with local recurrence or new polyps on colonoscopy.

The study will follow the new national guidelines with the approved acceptable timeframe adjustments, this meaning we will conduct the control colonoscopy at 3 months for piecemeal resection and a full colonoscopy at 1 year for all the patients involved in the study.

More than 90% of bowel cancers arise from adenomas and therefore prevention of adenomas is effective in preventing colorectal cancer.

**Method**: We aim to include and randomize 400 patients at the four institutions into two groups of equal size. It is expected that 80% of those will comply throughout one year of treatment. The patients are randomized blindly into one group receiving daily 100 ml active carrot juice and one group receiving 100 ml placebo. This amount has been calculated from our experiments in rats to be a sufficient volume as measured by serum concentration. After 1 year, we will register the number and sizes of polyps diagnosed in the 2 groups.

The primary aim is to investigate for a carrot-medicated inhibition of neoplastic transformation and growth in high risk humans.

# Background:

The polyacetylenes falcarinol and falcarindiol can be found in vegetables, and particularly in certain varieties of carrots. The level of polyacetylenes varies greatly in different carrot cultivars and varieties (2). Preliminary investigations suggest that the content of falcarinol and falcarindiol is higher in the older cultivars of carrots than in the modern, sweeter commercial varieties. The content of falcarinol and falcarindiol of carrots also depends upon exposure to light and temperature during storage (2). Acceptable conditions of storage have been established.

The biological effects of falcarinol and falcarindiol have been studied in almost 30 years at University of Southern Denmark, Department of Surgery, Odense University Hospital and the Department of Food Science, Aarhus University. It has been established that (1, 4-9):

1. Falcarinol and falcarindiol can be purified in a stable form.

2. Falcarinol inhibits the growth of human cancer-cells in vitro, and the effect is enhanced by adding falcarindiol.

3. Freeze dried carrots, purified falcarinol and purified falcarinol and falcarindiol inhibits the formation of adenomas (cancer precursors) in the bowel of rats primed to develop colon cancer with the carcinogenic compound azoxymethane by 30 - 80 %.

4. Falcarinol and falcarindiol inhibits the growth rate of adenomas in the same rats.

5. A serum level comparable to that of the rats can be achieved in human volunteers by eating 200-400 gram of carrots daily corresponding to 100 ml of carrot juice or smoothies. More than 30 cultivars have been grown for 4 different seasons and varieties with a high content has been identified. These include the purple "Night Bird" used in previous studies and a new candidate "Yellowstone". Night bird is not commercially available any more. The yellow "Yellowstone" is equal in content and will be used in this study.

6. A method for measuring Falcarinol in human blood and other sources such as carrot juice has been developed and published.

7. Conservation methods and storage conditions with no, or very limited loss of active substances has been established.

8. Correlation between oral intake and serum levels and the pharmacokinetics has been determined in healthy volunteers and published.

9. It is known that polyacetylenes has an anti-inflammatory effect and inhibits the Cox receptors and some interleukins such as TNF $\alpha$ , IL-6 and IL1 $\alpha$  in humans. One action of polyacetylenes is therefor similar to aspirin (non-selective COX inhibitor) and pharmaceutical COX 2 inhibitors (Celecoxib), which is known to exhibit a

prophylactic effect against the formation of colon cancer in humans. They have also been suggested as adjuvant treatment to patients with colorectal cancer to prevent recurrence.

10. Proteomic analysis have strongly indicated that patients can be divided into 3 groups according to their genomic profile to be high, medium or low in susceptibility to COX2 inhibition indicating a possible road for personalized prevention.

The aspirins are not in general use for cancer prophylactics because it induces stomach- and duodenal ulcers and the selective COX 2 inhibitor is not used mainly because they increase the risk of cardiac failure related mortality. This has been ascribed to suppression of serum prostacyclin. None of these side effects have been described after the intake of carrots, but treatment with purified carotene has been described to increase the risk of cancer development in the prostate. The polyacetylenes from carrots and their interaction with human cancer cells and enzyme systems have been systematically investigated and published during the last 15 years from our study group and others (1, 4-9).

We have conducted 3 studies in rats where we confirmed a statistical significant reduction of neoplastic developments in the forms of both aberrant crypt foci and adenomas; and a reduced growth velocity of these neoplasms (6,8,9). The rats were given both falcarinol and falcarindiol, and the prophylactic effect found in earlier studies on falcarinol only was confirmed and synergistically enhanced to the same level as freeze dried carrots. The reduction of early neoplasms was in the order of 35 % increasing to 80 % for later stages of neoplasms (large adenomas). One of our later studies conformed a dose-response in the azoxymethane induced rats and gave the basis to determine the lowest therapeutic level necessary to achieve a maximal prophylactic effect.

Overall, the available evidence suggests that regular consumption of FaOH/FaDOH rich carrots should have a protective effect on colorectal cancer in humans. The research field is still relatively new and despite the fact that the necessary FaOH/FaDOH concentrations are easily achieved in humans, no randomized clinical human trials has been conducted.

### Project description for a human trial on colorectal cancer prophylaxis:

#### Aim:

Primary aim:

To investigate for a possible inhibitory effect from carrot juice on the recurrence of excised adenomas and, on the formation of metachronous adenomas in patients who are enrolled in a follow up program after resection of high risk colorectal adenomas.

An inhibitory effect of carrot juice will be measured by a combined endpoint of total number of recurrent adenomas multiplied with mean size of recurrent adenomas in the active arm or the placebo group. This difference will be significant if carrots mediate a 20% reduction in both size and numbers.

If the difference in number of polyps is 40 % or more, we will be able to prove this to be significant. If the difference in polyp size is larger than 40 % we will also achieve statistical difference between the 2 groups.

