#### **Outcome measures**

Primary:

• The primary outcome is the number and size of polyps found at the one-year follow up colonoscopy in the treatment arm and in the placebo arm.

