#### Secondary:

- Number of patients with polyps in the two arms
- Polyp number and size in relation to level of compliance to treatment.
- Risk stratification of polyps identified at follow up in each arm.
- Number of polyps with low, medium and high degree of dysplasia and cancer.
- Compliance, side effects and acceptability of treatment.
- User preference of carrot intake across patient profiles and carrot products.

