#### Sample size:

Patients seen at the one-year follow up after high risk polyps have 40 % chance of having new polyp/polyps at the colonoscopy. The difference in polyp number found between treatment and control in rats was 40%. The difference in large polyps was 80 % but this is based upon small numbers. The possible effect in humans is unknown. A difference of 10 % or 20 % would be of clinical interest. To test for a difference of 20 % would demand the enrolment of 1248 persons, which is not realistic.

The study is dimensioned to prove a significant difference in number of polyps after 3 years and a significant difference in the combined endpoint (number x size) after 1 year of treatment. The expected effect in number of adenomas in the active and the control arm is a > 20% reduction (corresponding to a 50% relative reduction).

- 1. The recurrence rate is estimated to 40%
- 2. The acceptance rate to participate is 55%.
- 3. The exclusion rate is 20%
- 4. The total drop-out rate is expected to be 20%.
- 5. The drop-out patients are estimated to an average 6 months participation.

We assume 80% power and a standard deviation of 5%. Using a two-sided X2-test, a total of 726 patients have to be invited with a minimum of 328 patients to complete the trial. Due to the expected variability of the factors above, we aim to include a total of 400 patients equally to either case or controls. Achieving this number of included patients will require approximately 1.000 possible candidates to be invited. The combined capacity of the included centers is 1.600 eligible patients per year. Therefore, we estimate that the enrollment can be completed within 12 months.

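### The 1-year primary endpoint is stated inconsistently, and the chi-square sample size neither matches it nor reproduces the stated 328, so significance for a 20% reduction in both size and number is unsupported

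*Protocol*

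**What the plan says.** Four parts of the protocol bear on the primary result.

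- **Aim.** The aim covers both recurrence of excised adenomas and new (metachronous) adenomas. The yardstick for the effect is this: "a combined endpoint of total number of recurrent adenomas multiplied with mean size of recurrent adenomas in the active arm or the placebo group". The section then states: "This difference will be significant if carrots mediate a 20% reduction in both size and numbers". It makes similar promises for number alone and size alone at 40%.
- **Outcome measures, primary.** "The primary outcome is the number and size of polyps found at the one-year follow up colonoscopy", by arm. There is no product, and the lesion is now a polyp.
- **Outcome measures, secondary.** The list includes "Number of patients with polyps in the two arms". It does not include a 3-year number.
- **Sample size.** "The study is dimensioned to prove a significant difference in number of polyps after 3 years and a significant difference in the combined endpoint", the latter at 1 year. The inputs are a 40% recurrence rate, an effect given as more than a "20% reduction (corresponding to a 50% relative reduction"), 20% drop-out and 55% acceptance. "We assume 80% power and a standard deviation of 5"%, with no variable named. The result is: "Using a two-sided X2-test, a total of 726 patients have to be invited with a minimum of 328 patients to complete the trial". The trial aims to include 400, split equally. Alpha is not stated.

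**The concern.** The Aim and Sample size sections agree that number times size at 1 year is the combined endpoint. Outcome measures, where a reader looks for the primary, does not contain it. As written in the Aim, the endpoint is a total times a mean for each arm. That gives one value per arm, so it has no variance to test until it is defined for a patient.

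The sample size uses a test of two proportions. It therefore sizes a different variable, one that the protocol ranks as secondary. The Aim nevertheless promises significance for the product at a named effect.

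Two things are at stake. Product, number or size, and adenomas or any polyp, could each be presented as the primary result once the data are seen. And a null result could be read as absence of effect when the chance of detecting the named effect was never worked out.

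**Working it through.** **Inputs from the protocol (Sample size, Aim):** control rate 40%; treated rate 20% (20 points, 50% relative); power 80%; two-sided chi-square; 1:1 allocation; drop-out 20%; acceptance 55%; target for the product 20% off both number and size. **Assumed:** alpha 0.05.

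**1. The stated 328.** With the pooled two-proportion formula and p̄ = 0.30,

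n per arm = [1.96·√(2·0.30·0.70) + 0.842·√(0.40·0.60 + 0.20·0.80)]² / 0.20² = 81.2, rounded up to 82.

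The total is 164 (182 with continuity correction). The stated 328 is twice 164. With 164 per arm, power for 40% against 20% is 97.9%, not 80%.

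**2. Nearest match.** A 20% fall in both number and size leaves 0.8 × 0.8 = 0.64 of the product, a 36% fall. Applied to the recurrence rate, 40% × 0.64 = 25.6%. For 40% against 25.6% at 80% power, the total is 326 (unpooled variance) to 332 (pooled), which brackets 328. The protocol does not state this input. If it was used, the fall in a product was entered into a test of a proportion.

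**3. Enrolment chain.** 726 × 0.55 = 399 enrolled. 400 × 0.80 = 320 completers, 8 below the stated minimum of 328.

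**4. The 5% standard deviation.** In a chi-square test of two proportions the variance is p(1 − p), fixed by the rates. No separate standard deviation enters.

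**5. Power for the product as a patient-level quantity.** The protocol gives no mean or variance for number, size or product, so this is an illustration over a range. Let burden be zero without recurrence. Among patients with recurrence, let it have mean m and coefficient of variation CV. A proportion p has recurrence. Then

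mean = p·m; variance = p·m²·(1 + CV²) − (p·m)².

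Control: p = 0.40, m = 1, mean 0.40. Two ways to reach the 36% fall:

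- A: p = 0.32, m = 0.8, mean 0.256
- B: p = 0.40, m = 0.64, mean 0.256

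The difference is 0.144. Power = Φ(0.144/√((V₁ + V₂)/n) − 1.96). For example, A with CV 1.0 and n = 160: V₁ = 0.640, V₂ = 0.344, ratio 1.836, power 45%.

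| Assumed CV | 160 per arm, A to B | 200 per arm, A to B |
|---|---|---|
| 0 | 84 to 88% | 91 to 94% |
| 0.5 | 71 to 75% | 80 to 84% |
| 1.0 | 45 to 48% | 54 to 57% |
| 1.5 | 28 to 30% | 34 to 36% |

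The CV at which power is 80% is 0.27 (A) or 0.39 (B) at 160 per arm, and 0.50 (A) or 0.58 (B) at 200 per arm.

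**The case against.** The best defence is that two of the three sections do agree on number times size at 1 year, and that some of the shifting between adenoma and polyp, or recurrent and new, is loose wording. That stands in part. Recurrent may be meant to cover new lesions. Adenoma against any polyp remains a real difference in what is counted.

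A second defence is that 328 may have been derived for the Aim's own target, through 40% against 25.6%. This is plausible, but it is a back-calculation from an input the protocol does not give, and it would not make a test of proportions valid for a product.

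A third is that every power figure for the product rests on assumed distributions, and that the test may be fixed in an analysis plan not seen here. That stands. With other assumed count and size distributions, simulated power was about 54 to 71% (Welch test) or 22 to 51% (Mann-Whitney test) at 160 to 164 per arm. At 200 per arm it was about 63 to 80% or 26 to 56%.

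Some stronger readings are tempting but unsupported:

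- **That the trial is underpowered by a known amount.** No variability is given, and at low variability power exceeds 80%.
- **That 164 patients would be enough.** That number serves a secondary outcome.
- **That an arm total will bias the comparison.** It does so only if the numbers examined differ between arms, and nothing in the protocol indicates that they will.
- **That the 5% describes patient-level burden.** The protocol ties it to no variable.

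**Conclusion.** The point holds and should be corrected before unblinding. Four findings rest on the text and simple arithmetic:

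- The 1-year primary is not stated as one quantity.
- The sample size is for the proportion of patients with polyps, a secondary outcome.
- The stated inputs give 164 patients in total rather than 328 (assuming two-sided alpha 0.05), and the 5% standard deviation has no role in the test.
- The planned enrolment with the expected drop-out gives 320 completers, short of the stated minimum.

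The Aim's statement that 20% off both size and number will be significant has no calculation behind it, and it also treats power as certainty. Whether power for that target reaches 80% depends on variability that the protocol does not give. The supportable conclusion is that 80% power is not assured, not that a particular shortfall exists.

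**What to change.** Amend the text before the code is broken.

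1. State one 1-year primary in identical words under Aim, Outcome measures and Sample size, with one lesion term and a patient-level definition. One option that keeps the sponsor's combined endpoint is the sum of adenoma sizes per examined patient, set to 0 if none is found. Other patient-level definitions would also serve.
2. Label the remaining quantities as secondary, including the 3-year number.
3. Delete or restate the sentences in the Aim that promise significance at 20% and 40%.
4. In Sample size, remove the 5% standard deviation. Replace the chi-square justification with the power that 400 enrolled (about 320 completers) gives for the chosen primary over a stated range of variability. State alpha. If the patient proportion stays as a secondary outcome, give its inputs and number consistently.

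The trial need not be enlarged, and no visits are added. The costs are that the restated power may fall below 80%, that number alone and size alone may lose primary status, and that the eCRF must link size to histology for each lesion if adenomas are the unit. The protocol does not say whether it does.

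### The combined primary endpoint is defined as an arm total with no per-patient value, so it moves with the number of patients examined and cannot be tested as written

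*Protocol*

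**What the plan says.** The Aim section of the protocol measures the inhibitory effect by a "combined endpoint of total number of recurrent adenomas multiplied with mean size of recurrent adenomas in the active arm or the placebo group". It adds: "This difference will be significant if carrots mediate a 20% reduction in both size and numbers". No patient-level value and no denominator is given there.

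The Outcome measures section lists the primary outcome as the "number and size of polyps found at the one-year follow up colonoscopy in the treatment arm and in the placebo arm". It does not use the word total, and it does not say how number and size are to be summarised.

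The Sample size section states "The total drop-out rate is expected to be 20" (per cent), with no split by arm. Its test is a two-sided chi-square on 400 patients allocated equally. That test implies a proportion of patients, but the section does not connect it to the combined endpoint.

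On retention the protocol points both ways. Design of the intervention says patients are followed whatever their compliance. The same section lets the project nurse exclude a patient judged non-compliant, and Common pathway excludes those with almost complete non-compliance. Common pathway also says all patients have a full colonoscopy at one year.

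**The concern.** A sum over an arm depends on two things: how much adenoma each examined patient has, and how many patients were examined. Only the first bears on the juice. If fewer active-arm patients reach the colonoscopy, the active total falls with no effect of treatment; if fewer placebo patients reach it, a real effect is partly hidden.

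The second difficulty is independent of drop-out. One total per arm gives two numbers and no measure of variation between patients, so the significance claimed in the Aim section has nothing to be tested against.

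Both difficulties lie in the definition of the primary endpoint. This is not a detail that the protocol leaves to the SAP, because the protocol writes out the formula.

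**Working it through.** **Inputs from the protocol.** 400 patients, 200 per arm, and 20% drop-out overall (Sample size); 20% fewer and 20% smaller adenomas (Aim).

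**Assumptions.** The split of drop-out by arm is not given, so a range is shown with the average held at 20%. Drop-out is taken to mean no one-year colonoscopy and to be unrelated to adenoma burden.

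**Step 1: what the product is.** Let an arm have N adenomas with sizes adding to S. Mean size is S/N, so number × mean size = N × S/N = S. The number of patients does not appear.

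**Step 2: the planned effect on this scale.** 0.8 × 0.8 = 0.64, a 36% reduction in the product. This is the benchmark for the shifts below. The protocol gives no sample-size figure for the product that could be reproduced; its 328 completers belong to the chi-square calculation.

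**Step 3: effect of unequal numbers examined.** With drop-out d in each arm,

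ratio of arm totals = true effect × (1 − d_active)/(1 − d_placebo).

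| Drop-out, active v placebo | Examined | Ratio of numbers examined | Apparent change, no effect | Apparent change, true 36% reduction |
|---|---|---|---|---|
| 20% v 20% | 160 v 160 | 1.000 | 0% | −36.0% |
| 22% v 18% | 156 v 164 | 0.951 | −4.9% | −39.1% |
| 25% v 15% | 150 v 170 | 0.882 | −11.8% | −43.5% |
| 30% v 10% | 140 v 180 | 0.778 | −22.2% | −50.2% |
| 15% v 25% | 170 v 150 | 1.133 | +13.3% | −27.5% |
| 10% v 30% | 180 v 140 | 1.286 | +28.6% | −17.7% |

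The last entry is 0.64 × 180/140 = 0.823.

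**Step 4: what it takes to imitate the planned effect.** A ratio of 0.64 with 320 examined in all needs 320/1.64 = 195 placebo and 125 active patients, that is, drop-out of 2.4% and 37.6%.

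**Step 5: chance alone.** With the same 20% drop-out risk in both arms, the standard error of the log ratio of numbers examined is √(2 × 0.2/(0.8 × 200)) = 0.05. The 95% range of the ratio is exp(±1.96 × 0.05), about 0.91 to 1.10.

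**Step 6: the per-patient version.** Dividing each arm's sum by its number examined cancels the factor in Step 3. The ratio is then 1.00 under no effect and 0.64 under the planned effect at every split, under the assumption that drop-out is unrelated to adenoma burden.

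**The case against.** The strongest reply is that the wording is loose and does not fix an analysis. A single total per arm cannot be tested, so the literal reading can hardly be what is meant. The chi-square in Sample size works on patients who complete, the secondary outcomes include the number of patients with polyps, and number and size are recorded at each patient's colonoscopy, so a per-patient analysis is available. This shows that the remedy is easy. It does not supply the missing definition: no section ties the chi-square to the combined endpoint or gives the endpoint a denominator.

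Some stronger readings are tempting, and here the reply is right:

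- **That Outcome measures also fixes a total.** It lists number and size by arm and says nothing about totals. Only the Aim section does.
- **That unexamined patients are scored as zero.** No section says so, and the handling of missing colonoscopies can properly be left to the SAP.
- **That the full 20% will go unexamined.** The Abstract speaks of 80% complying with treatment, and Design of the intervention uses drop-out for lapses in compliance. Common pathway plans the one-year colonoscopy for everyone. Part or all of the 20% may mean stopping juice.
- **That nothing protects balance.** Allocation is 50/50 within centre, the trial is double-blind, and taste is corrected so that the juices cannot be told apart. These make a large imbalance less likely. They do not exclude it, since non-compliant patients may also be removed after randomisation.

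**Conclusion.** The point holds as a defect in how the Aim section defines the primary endpoint. As written, the measure is the arm's sum of adenoma sizes. It has no between-patient variance, and the comparison is biased whenever the numbers examined differ.

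The size of the bias is conditional. Under the assumptions listed, a 4-point gap in drop-out moves the total by about 5%, a 10-point gap by about 12%, and an extreme 20-point gap by about 22%. In the opposite direction, the extreme gap cuts an apparent 36% reduction to 17.7%.

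A reader might set the 22.2% against the 20% reduction in number and conclude that drop-out alone could deliver the planned result. The documents do not support that. The quoted measure is the product, with a planned reduction of 36%, and Step 4 shows how implausible a split that would need. The lack of any variance to test depends on no drop-out assumption.

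**What to change.** In the Aim section, define the endpoint for each patient as the summed size of adenomas found at the one-year colonoscopy, with 0 for a patient examined and found clear. Give the number component as the adenoma count per patient. State that the mean per examined patient is compared between arms. Align Outcome measures with this wording, including whether adenomas or polyps are counted, since the two sections differ. Summed over an arm, the new quantity equals the present product, so the intended combination of number and size is kept.

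Two matters go with it. The statements on following patients regardless of compliance and on excluding non-compliant patients should be reconciled, because they determine who is examined. The SAP should say how randomised patients without a one-year colonoscopy are handled: dividing by the number examined removes the counting artefact, but not bias from drop-out related to adenoma burden.

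The cost is protocol wording. Number and size are already recorded at each follow-up colonoscopy, so no new data or patients are needed.

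### The protocol promises significance for number x size at a 20% fall in each, but its only sample-size calculation is for the proportion of patients with recurrence, and the contrast stated there does not give 328

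*Protocol*

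**What the plan says.** The Aim section measures the effect by a "combined endpoint of total number of recurrent adenomas multiplied with mean size of recurrent adenomas in the active arm or the placebo group", and adds: "This difference will be significant if carrots mediate a 20% reduction in both size and numbers". It also claims significance for a 40% difference in number alone or in size alone.

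The Sample size section says the study is dimensioned for two things: number of polyps after 3 years, and "a significant difference in the combined endpoint (number x size) after 1 year of treatment". It takes a recurrence rate of 40% and says the expected effect on adenoma number "is a > 20% reduction (corresponding to a 50% relative reduction"). It continues: "We assume 80% power and a standard deviation of 5" per cent. With a two-sided chi-square test, "a total of 726 patients have to be invited with a minimum of 328 patients to complete the trial". The target is 400 included, for which about 1,000 invitations are foreseen. The listed rates are 55% acceptance ("The acceptance rate to participate is 55" per cent), 20% exclusion and 20% drop-out, with drop-outs contributing 6 months on average. The same section says: "To test for a difference of 20 % would demand the enrolment of 1248 persons, which is not realistic". No alpha is stated.

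Under Outcome measures, the primary outcome is number and size of polyps at the one-year colonoscopy. The number of patients with polyps is secondary.

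**The concern.** The claim about the primary measure and the calculation behind the sample size concern different quantities. A chi-square test on two proportions says how many patients are needed to compare the share with any recurrence. It cannot test number times size, and its result carries no information on how variable that product is. The calculation also does not deliver its own headline figure from its stated inputs, so a reader cannot see what 328 was meant to detect.

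At stake is how a null result is read. Someone relying on the Aim section could take it as excluding a 36% lower adenoma burden, although the protocol has not shown that the trial could detect one.

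**Working it through.** **Effect claimed.** A 20% fall in each component gives 0.8 x 0.8 = 0.64, a 36% fall in the product. Total number times mean size equals the sum of all adenoma sizes in the arm: N x (sum of sizes / N). This is one value per arm, so a test needs the between-patient variance of the per-patient sum. The protocol gives none.

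**The figure 328.** Inputs: 40% recurrence, 50% relative reduction (so 20%), 80% power; two-sided alpha of 5% is my assumption.
- Pooled: n per arm = [1.960 x sqrt(2 x 0.30 x 0.70) + 0.842 x sqrt(0.24 + 0.16)]^2 / 0.20^2 = 81.2, so 82 per arm and 164 in total.
- Unpooled: 7.849 x 0.40 / 0.04 = 78.5, so 158 in total. Continuity-corrected: 90.9, so 182 in total.
- With 164 per arm (328 in total), power for this contrast is about 98%, not 80%.

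**What comes near 328.** Applying the 36% fall to the recurrence rate gives 40% versus 0.40 x 0.64 = 25.6%.
- Unpooled: 7.849 x (0.24 + 0.1905) / 0.144^2 = 162.9, so 326 in total. Pooled and arcsine both give 332 (continuity-corrected, 360).
- Power at 164 per arm is 79.6%.
- Other unstated inputs also come close: 40% versus 25% with continuity correction gives 330.

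**The standard deviation of 5%.** The variance of a proportion follows from the proportion itself, p(1 - p), so the chi-square calculation has no place for a separate standard deviation.

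**The figure 1248.** A 20% drop-out with half participation is an effective loss of 10%. For 40% versus 32%, unpooled: 7.849 x (0.24 + 0.2176) / 0.08^2 = 561.2 per arm; 561.2 / 0.9 = 623.5, rounded up to 624; total 1248. The match is exact, so 20% is relative here. Where a reduction above 20% is expected and equated with 50% relative, 20% is absolute (40% to 20%).

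**Number alone.** At 400 x 0.8 = 320 completers (160 per arm), 40% versus 32% gives z = (0.08 x sqrt(160) - 1.960 x sqrt(2 x 0.36 x 0.64)) / sqrt(0.4576) = -0.47, a power of about 32%. Measured as the protocol's own calculation measures it, a 20% fall in number is out of reach alone. The Aim section's claim therefore depends on what size adds.

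**Invitations.** 726 x 0.55 = 399; x 0.8 for drop-out = 319; x 0.8 again for exclusion = 256. With all three rates, 328 completers need 328 / (0.55 x 0.8 x 0.8) = 932 invited. The 1,000 invitations give 1,000 x 0.55 x 0.8 x 0.8 = 352.

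**Can power for the product be bounded?** Not from the document. If 60% of control patients have no adenoma, the coefficient of variation (CV) of the per-patient sum is at least sqrt(0.6 / 0.4) = 1.22. By a normal approximation with equal CVs, 80% power for a 36% fall at 160 per arm needs a CV of at most sqrt(160 x 0.36^2 / (7.849 x (1 + 0.64^2))) = 1.37. Whether that is met depends on counts and sizes the protocol does not describe. Simulations with assumed counts (one lesion per recurrent patient, Poisson or negative binomial) and assumed size CVs of 0.25 to 1.0 gave 41% to 80% with mean-based tests and 18% to 71% with a rank test at 160 per arm. With identical sizes, the upper ends rise to about 85% and 97%. The width of these ranges is the result: the answer is set by the assumptions.

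**The case against.** The strongest reply is that 328 may be a rough sizing for the combined endpoint after all, with the recurrence rate as proxy: 40% versus 25.6% needs 326 to 332, and the promise of significance may be shorthand for the 80% power stated later. This is plausible and weakens any suggestion that 328 is arbitrary. It does not repair the protocol. That contrast is nowhere stated, the one that is stated (50% relative) gives about 164, and a comparison of proportions would not give the power for number times size.

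Three further points stand. The figure 1248 is sound once the half-participation item is used. Recruitment planning does not rest on 726, because the 1,000 invitations would yield more than 328 completers. And the Aim section's separate claim for a 40% difference in number is reasonable if read as 40% versus 24% of patients (about 87% power at 160 per arm).

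A statistical analysis plan could supply the test and variance model, but the protocol itself makes the claim and fixes the numbers.

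A reader might infer that the trial is underpowered, that 328 came from doubling 164 by mistake, or that 320 expected completers against a minimum of 328 is a material shortfall. The documents support none of these. No variance is given from which to show underpowering. Doubling is only one of several possible origins of 328. The gap of 8 is about 2.4% and hardly moves power.

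**Conclusion.** The statement in the Aim section is wrong as written: it asserts significance for the primary measure without any calculation for it, and no sample size makes significance certain. The supporting section sizes a secondary outcome. On its stated contrast it gives 158 to 182 completers, not 328, if alpha is two-sided 5%. The 5% standard deviation has no meaning in that calculation, 726 invited leads to 319 or 256 completers, and 20% is used on two scales.

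Power for number times size is not shown; neither a particular power nor a shortfall is established. For the contrast it states, 328 is more than enough. The point should be fixed before the protocol is relied on, because it concerns the justification of the primary endpoint.

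**What to change.** In the Aim section, replace the promise of significance with the power, or the detectable reduction, for number times size at the expected number of completers. Base it on patient-level variance, for example of the per-patient sum of adenoma diameters (0 if none), with the count and size assumptions stated and a range shown.

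In the Sample size section:
- state alpha, the outcome and the two rates behind the chi-square test;
- restate 328, or show the inputs that give it;
- remove the 5% standard deviation or say what it describes;
- mark each 20% as relative or absolute;
- correct 726, or reconcile it with the listed rates and the 1,000 invitations;
- reconcile the 3-year sizing statement with the 1-year primary outcome.

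The cost is wording and a restated calculation. Counts and sizes are already recorded at the one-year colonoscopy (Common pathway), so no patients or data are added. The downside is that the stated detectability may be less favourable than the present text suggests.
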